### Preliminary Studies:

**Methods:** OSA patients (AHI>20, age 20-65) acclimated to CPAP were studied while sleeping with CPAP, or on the third night after CPAP withdrawal. During sleep, from 10:40 PM to 6:40 AM, we measured serum FFA, glycerol, insulin, glucose, and triglycerides every 20 minutes via an indwelling IV. Upon awakening, we performed an oral glucose tolerance test (OGTT) and peripheral artery tonometry (EndoPAT) to assess reactive hyperemia index (RHI). We compared effects of OSA versus CPAP in the same subjects on two different nights, one to 4 weeks apart. **Results:** 18 patients (13 men, 5 women) completed most aspects of the study to date. CPAP withdrawal led to re-emergence of OSA (CPAP AHI:  $4.9\pm0.9$ , vs. OSA AHI:  $66.7\pm7.5$ ; mean  $\pm$  SEM,  $p<0.001$ ). Fig. 1

[figure not shown]

**Figure 1. OSA increases nocturnal FFA, glucose, and insulin.** Blood was sampled at 20 min intervals beginning at 10:40 PM (lights out) until 6:40 AM (lights on, dashed line). The same 18 patients were studied asleep wearing CPAP (red) or with OSA (on the third night after stopping CPAP, blue). Lines depict mean  $\pm$  SEM.

demonstrates that OSA also increased nocturnal FFA, glucose, insulin, and triglycerides (trend) compared to CPAP. Glycerol measured in 7 subjects was also elevated (CPAP:  $0.17 \pm 0.06$ ; OSA:  $0.29 \pm 0.11$  mmol,  $p=0.04$ ) confirming adipose tissue lipolysis during sleep. While RHI did not differ between CPAP/OSA, the extent of FFA elevation correlated with the decrease in RHI ( $r=0.51$ ,  $p<0.05$ ).

Mixed model analysis demonstrated that the nocturnal FFA dynamically changed with heart rate, but not with apnea hypopnea index (AHI),  $\beta=0.0043$  mmol per 1 BPM increase (CI: 0.001-0.0067;  $p=0.008$ ) after adjustment for AHI and BMI. This suggests that SNS activation may be the cause of lipolysis and hyperglycemia. In mice, we showed that exposure to intermittent hypoxia caused lipolysis, hyperglycemia, hyperlipidemia, and glucose intolerance, and many of these findings were abolished by propranolol [2]. Hence, the autonomic response to OSA, not a high AHI or low oxygen level *per se*, elicits excessive lipolysis, insulin resistance, and hyperglycemia during sleep. This physiology is consistent with the effects of OSA on blood pressure [18, 19] and the role of catecholamines in lipolysis, insulin resistance, and hyperglycemia in other forms of physical or emotional stress [20, 21].

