**Each sleep study night will consist of the following procedures:**

*Pre-sleep procedures.* Subjects will undergo a history and physical examination. They will report to the CRU at 4:00 PM and undergo anthropometric assessment including weight, height, neck, and waist circumference. At 5:30 PM, they will eat a standard dinner containing 30% fat, 50% carbohydrate, and 20% protein with kcal based upon the Mifflin-St Jeor formula. Two peripheral IVs (18 to 20 gauge) will be placed. All samples are obtained through the IV without disturbing the subject during sleep. Blood pressure will be checked at 6:30 PM, before administration of study drug. If systolic blood pressure is <90 or the heart rate is <50 then no drug will be administered. (In the event that this occurs, the study will still proceed so that CPAP and OSA nights can be compared and analyzed as a "no drug" group.) If blood pressure and heart rate are acceptable, propranolol LA 80 mg, or placebo (random order, crossover on study night 2 and 3) will be given. Participants and the investigators will be blinded to drug assignment.

*PSG setup.* On each study night from 10:30 PM until 6:30 AM, a PSG will be performed. The sleep study will include electroencephalography, electrooculography, oxygenation, respiratory effort, CPAP airflow, and transcutaneous CO2 monitoring. Respiratory effort will be measured by thoraco-abdominal movement assessed by mercury strain gauges. Surface electrodes will be placed at C3A2 and C3O1, a submental electrode, and left and right electro-oculogram will be used to stage sleep. Electrocardiograph (EKG) tracings will be recorded from three chest electrodes. Continuous measurement of oxygen saturation will be recorded using an ear oximeter (model No 472-1A, Hewlett Packard, Waltham, Mass). Transcutaneous CO2 will be monitored using a Radiometer TCM-4 device. Signals from the electroencephalograph, EKG, electromyogram, electrooculogram, respiratory strain gauge, ear oximeter and thermistors will be recorded on a computer with RemLogic software.

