In total, the blood collected will be approximately 30 samples x 4 mL = 120 mL. For patients that consent to isolation of genetic material, the total will be 136 cc. This quantity is less than half the volume of blood given during a donation (350 mL). A morning urine sample will be collected for measurement of catecholamines. The final blood sample will be drawn at 9 AM, after which the IV will be removed, and the subject will be discharged from the CRU. Samples will be frozen at -80°C for research pertaining to metabolic effects of OSA, with the consent of participants.

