## **5. Inclusion/Exclusion Criteria**

This study is similar to "MIIC: Metabolic Impact of Intermittent CPAP" (NA\_00086830) in terms of CPAP withdrawal procedures. Thus, inclusion/exclusion criteria are similar but are expanded to exclude patients with contraindications to taking beta blockers. In addition, we are attempting to enrich the cohort with participants who exhibit high FFA or glucose levels during CPAP withdrawal. Participants who completed their involvement in MIIC, who have resumed CPAP for at least 1 month, may enroll in this study. They must have exhibited a FFA or glucose elevation of  $\geq 10\%$  during their CPAP withdrawal study.

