**Inclusion Criteria:**

1. Men and women of all races  $\geq 20$  and  $\leq 70$  years old
2. History of OSA (AHI $>20$ ,  $>50\%$  events obstructive)
3. Accustomed to CPAP use, and willing to discontinue CPAP temporarily for the study and switch to NDS
4. If the participant has already completed "Metabolic Impact of Intermittent CPAP" (NA\_00086830, they must have exhibited a  $>10\%$  increase in nocturnal FFA or glucose during CPAP.

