Stable isotopes [ $^2H_{31}$ ]palmitate and  $H_2^{18}O$  will be used to follow the fate of ingested fat (palmitate), and to quantify the plasma water pool size to permit calculation of tracer oxidation rate. This is a validated technique to quantify FAO by providing an oral liquid dose of [ $^2H_{31}$ ] palmitate taken with dinner [53]. We will administer [ $^2H_{31}$ ] palmitate orally with dinner in a liquid emulsion (such as an Ensure® shake) at a dose of  $15 \text{ mg/kg}$  body weight (approximately  $1.7 \text{ g}$  of fat for a  $120 \text{ kg}$  person, Cambridge Isotope Laboratories DLM-215-MPT). In addition, we will administer a stable isotope of water, [ $H_2^{18}O$ ] 10% orally at a dose of  $0.4 \text{ g/kg}$  body weight (about  $48 \text{ mL}$  for a  $120\text{-kg}$  person, Cambridge Isotope Laboratories OLM-240-10-0). When [ $^2H_{31}$ ]palmitate is oxidized, the  $^2H$  is released into the plasma  $^2H_2O$  and is quantified by mass spectroscopy.

**b. Justification and safety information if FDA approved drugs will be administered for non-FDA approved indications or if doses or routes of administration or participant populations are changed.**

We will be administering unmodified, marketed product via the typical oral route at a standard clinical dose. This proposal was presented the FDA and qualified as exempt from IND application (see separate documentation). Propranolol is FDA approved for indications including hypertension, migraine, supraventricular tachycardia, and essential tremor and lawfully marketed in the United States. This research is not intended to support any change in the advertising or labeling of the drug. A conventional starting dose of drug is being administered, and the drug will be administered one time during the study. The investigator will not represent the drug in any promotional context, distribute, test-market, or charge for the drug.

Propranolol is a non-selective (beta-1 and beta-2 receptor), non-vasodilating beta adrenergic receptor antagonist. It has been used for decades for hypertension and angina as well as "off label" for other

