- Isotope infusion and ingestion: Stable isotopes are naturally occurring, non-radioactive compounds normally present in the body at low levels. Infusion or ingestion of isotopes at very low tracer doses transiently increases the level of these molecules by <10% and is not associated with any adverse effects. As is the case with any infusion, there is a small chance of infection.
- DEXA scan: DEXA scans are considered safe and deliver minimal radiation.
- Venipuncture: May be associated with discomfort and bruising.

Phlebotomy: In total, the blood collected will be approximately 116 cc (as compared to approximately 350 mL during a donation). Theoretically, if too much blood is lost, this could lead to low blood pressure and cardiovascular stress or dizziness.

- Nasal dilator strips: These are non-latex, adhesive tape applied to the nose designed to mitigate snoring and nasal congestion. There may be discomfort using NDS and they are likely to be inferior to CPAP for treating OSA.
- Confidentiality of genetic material: There is the risk that genetic data is revealed outside the study. Information can also lead to unwanted psychological or financial consequences if it were released to a third party.

b. Steps taken to minimize the risks.

- Withdrawal of CPAP: The period of withdrawal is kept relatively short, at 3 nights. Subjects will be advised to arrange transportation home so that they do not need to drive. They will be advised to increase their total sleep time, if necessary, during CPAP abstinence to minimize sleep deprivation off CPAP. On the day of the non-CPAP sleep study, if they plan to drive home themselves, they will be provided with an additional 3-4 hours of time in the lab to sleep before discharge. Patients at increased cardiovascular risk (uncontrolled hypertension, heart failure) are excluded. Participants with high-risk occupations requiring vigilance, such as commercial drivers and pilots, will be excluded. Participants who have ever been in a near-miss or motor vehicle accident due to sleepiness will be excluded. When communicating with patients about their off-CPAP visits, patients will be asked in the 1-2 days before their visit if they have experienced any near-miss events or motor vehicle accidents. If they have, then they will be excluded from the study, advised to resume CPAP immediately, and to avoid driving or other high risk activities until they have used CPAP for 3 nights.

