- Propranolol: Risks are minimized by providing only a single dose of drug at a low clinical dose. We will exclude patients with contraindications to the drug or those who are taking medications that affect (or are affected by) propranolol metabolism. We will exclude elderly (>65 years old) in whom propranolol LA has not been well studied. We will monitor blood pressure and heart rate during the study. We perform a screening EKG to exclude those with underlying conduction or rhythm disorders. The EKG will be reviewed by [name], [name], or [name]. All physicians are board certified in pulmonary and critical care medicine. If a conduction or rhythm abnormality is detected (see exclusion criteria) the participant will be informed of the finding. With the participant's consent, we will also provide a copy of the EKG to the patient, the patient's primary care provider or cardiologist, and provide them with contact information for the Johns Hopkins cardiology clinic for further evaluation. Any unstable arrhythmia such as sustained wide complex tachycardia, atrial fibrillation with rapid ventricular response, or complete heart block will be dealt with as a medical emergency with transfer to the emergency room. In terms of bronchospasm, patients with a history of asthma (no worse than mild intermittent as per NHLBI 2007 guidelines) including those on regular controller medications will be excluded.

- Isotope infusion and ingestion: To mitigate any chance of infection from infused isotopes, they will be compounded in a sterile facility by a registered pharmacist. The infusion is also filtered through a 22 micron (Millipore) filter during infusion. The patient will be monitored for any infection or allergic reaction to the infusion, and the infusion stopped in the event of the development of symptoms such as urticaria, flushing, nausea, fever chills.
- Venipuncture: Discomfort, bruise formation, and infection will be minimized by use of sterile supplies and aseptic technique by trained personnel.
- Phlebotomy: The volume of each blood draw is minimized to balance safety with the need to obtain a useful amount of plasma after centrifugation. The risk of inducing hemodynamic or cardiovascular stress is minimized by excluding those with significant baseline anemia (hemoglobin <10 mg/dl). Those found to have anemia will be informed of the results and advised to seek medical evaluation as appropriate.

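### Inclusion criterion 1 admits people up to age 70, but protocol section 8b tells the IRB that people over 65 are excluded on propranolol-safety grounds

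*Protocol*

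**What the plan says.** Protocol section 5, inclusion criterion 1, sets the age range: "Men and women of all races $\geq 20$ and $\leq 70$ years old". The exclusion list that follows covers cardiovascular risks, interacting drugs, other medical conditions and driving risk. None of its items sets an age limit.

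Protocol section 8b, under the steps to reduce propranolol risk, states: "We will exclude elderly (>65 years old) in whom propranolol LA has not been well studied".

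Two other places bear on the question without answering it. The preliminary study in section 3 used a narrower range: "OSA patients (AHI>20, age 20-65) acclimated to CPAP were studied while sleeping with CPAP". The introduction to section 5 relates this trial's rules to those of an earlier CPAP-withdrawal study: "inclusion/exclusion criteria are similar but are expanded to exclude patients with contraindications to taking beta blockers". It does not say whether the age range was carried over or changed. The SAP gives no age limit.

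**The concern.** Both statements are current protocol text, and they give different answers for the same person. A 68-year-old is eligible under section 5 and excluded under section 8b.

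This is more than loose wording, because the limit of 65 comes with a safety reason: limited experience with the long-acting formulation in older people. The IRB is told of it as a protection. Section 5, where staff would look to decide eligibility, does not carry it. So either the promised protection is not in operation, or section 8b describes one that no longer applies.

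Two other provisions depend on the answer. Section 4 removes participants who turn out to be ineligible, and that rule cannot be applied consistently with two limits. Section 4c also allows the dose to rise from 80 to 120 mg after the first six participants, so the age question may apply to a higher dose than the starting one.

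**Working it through.** No calculation in the plan depends on this point, so the check is a comparison of text.

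**Inputs**
- Section 5, inclusion 1: lower limit 20, upper limit 70, both ends included.
- Section 5, exclusion items 1 to 4: no age limit.
- Section 8b, propranolol: over 65 excluded.
- SAP: no age limit.

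**Comparison, with age in completed years**

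| Age | Section 5 | Section 8b | Consistent? |
|---|---|---|---|
| 20–65 | eligible | not excluded | yes |
| 66–70 | eligible | excluded | no |
| 71 and over | not eligible | excluded | yes |

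The width of the disputed band is 70 − 65 = 5 years, that is, ages 66, 67, 68, 69 and 70.

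**Can other text settle it?**
1. The 20–65 range in section 3 describes who was in the preliminary study. It is not a rule for this trial.
2. Section 5 calls the criteria similar to those of the earlier study, which allows for a changed age limit as much as a retained one.
3. Section 6b argues for safety in general terms (a conventional starting dose, given once) and does not mention age.

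None of these decides between 65 and 70.

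**Does any statistic move?** The protocol sample size rests on a difference in free fatty acid levels, and the SAP sample size on a difference in heart rate. Neither uses age. The drug comparison is within person, so each participant's age is the same under propranolol and placebo. Age enters only as one adjustment variable in the multiple regression of protocol section 7c. There the limit would change the range of the variable but not the model.

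**The case against.** The strongest reply is that both sentences can be obeyed together: a person must be no older than 70 and must also pass the section 8b exclusion, so the working limit is 65. That is the cautious reading, and it is possible. It does not remove the need for a correction. The stated limit of 70 would then have no effect, and anyone screening from section 5 alone would not know of the stricter rule.

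A second reply is that participants are well protected whichever limit applies. This has force:
- Propranolol is given once, after a screening EKG (which may be deferred if a clinical EKG within the past year shows no listed conduction disorder).
- Section 5 excludes postural hypotension, decompensated heart failure, rhythm and conduction disease, interacting drugs, and chronic renal or liver failure. It also excludes systolic pressure below 90 or heart rate below 50 at screening.
- On the night, the same thresholds apply before dosing: "If systolic blood pressure is <90 or the heart rate is <50 then no drug will be administered". Section 7d stops the study night early if they are crossed after dosing, and the EKG is recorded during sleep.

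These safeguards reduce the likely consequence of dosing someone aged 66 to 70. None is specific to age, and section 8b presents the age exclusion in addition to them.

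A reader might also infer that the protocol offers no safety case at all for ages 66 to 70, because section 6b asks for one "if doses or routes of administration or participant populations are changed". That goes too far. The heading concerns approved drugs used outside their approved indications, or with changed doses, routes or populations. Whether this age band is a changed population cannot be judged without the label, which is not part of the documents. Section 6 does justify the dose for everyone enrolled, and it refers to separate documentation. What is missing from the text is an age-specific justification.

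**Conclusion.** The inconsistency is real and should be corrected. It concerns who may receive the study drug, and one of the two statements is a protection described to the IRB. Its size is five years of age, 66 to 70, assuming age is counted in completed years. The number of participants in that band cannot be stated, because no age distribution is given.

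Three stronger conclusions may be tempting, but the documents do not support them:
- A reader might infer that people over 65 have been dosed or harmed. Nothing in the documents shows that anyone in this band was enrolled.
- A reader might infer that the limit was raised from 65 to 70 and section 8b was not updated. The 20–65 range of the preliminary study fits that account but does not confirm it, and the intended limit remains unknown.
- A reader might infer that dosing a person of 66 to 70 would be a serious adverse event that halts the trial, since the definition in section 8c includes breaches of protocol and section 7d discontinues the study for serious events. The protocol does not class an age deviation that way, and with section 5 as written it is unclear that any breach would have occurred.

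The point does not bear on the validity of the treatment comparison.

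**What to change.** Change inclusion criterion 1 to an upper limit of 65, keeping the lower limit of 20, so that the screening rule applies the protection stated in section 8b. This needs only a short text amendment. Its cost is the loss of candidates aged 66 to 70. How much that would slow recruitment cannot be estimated from the documents. The SAP still plans 14 additional participants towards a total of 19, so under that plan the corrected rule would govern most enrollment.

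If 70 is the intended limit, remove the section 8b sentence and give the IRB an age-specific safety justification for dosing at 66 to 70, preferably in section 6b. It should also cover the possible increase to 120 mg. The cost is a brief added safety argument and its review.

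Either way, sections 5 and 8b should state the same limit.

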## **9. Benefits**

a. Description of the probable benefits for the participant and for society.

There are no direct benefits to participants for being in this study. This study will help researchers learn whether propranolol attenuates glucose or FFA elevations caused by OSA, which will demonstrate the potential mechanism by which OSA may foster diabetes and cardiovascular disease.

## **10. Payment and Remuneration**

a. Detail compensation for participants including possible total compensation, proposed bonus, and any proposed reductions or penalties for not completing the protocol.

Participants will be paid up to \$1000 for completing all parts of this study, based on the following procedures:

- \$250 for each sleep study (3 visits) = \$750
- \$25 for each EndoPAT test (done after each of the 3 visits) = \$75
- \$50 for a DEXA scan (only done once)
- \$125 study completion bonus for participants who are able to keep their appointments as originally scheduled. They will forfeit this bonus if they must reschedule their visit(s).
- They will also receive parking reimbursement so there is no fee to come to our laboratory
- NOTE: If a participant has completed parts of the study before this change in research is approved, we will still offer them the increased payment system above.

## **11. Costs**

a. Detail costs of study procedure(s) or drug (s) or substance(s) to participants and identify who will pay for them.

Participants will not be billed for study procedures. Polysomnograms and blood tests will be billed to the study at standard CRU rates.

Propranolol for Sleep Apnea Treatment (PROSAT)

NCT03049306

April 25, 2023

PROPRANOLOL FOR SLEEP APNEA THERAPY (PROSAT)

STATISTICAL PLAN

April 25, 2023

Developed by:

[figure not shown]
[figure not shown]
[name], Division of Pulmonary and Critical Care Medicine

[name], Johns Hopkins School of Public Health

Background:

20 million adults in the United States and >100 million adults worldwide have OSA, and the prevalence continues to rise with obesity. These figures are especially alarming as OSA is associated with cardiovascular disease and mortality. However, mechanisms linking OSA to these outcomes are unclear. As a result of this knowledge gap, fundamental questions such as what features of OSA are most harmful, and which patients can safely decline treatment, cannot be answered. Moreover, therapies for OSA such as CPAP are poorly tolerated, leaving non-adherent patients susceptible to CVD. We have observed that OSA acutely elevates nocturnal heart rate, morning blood pressure, and morning augmentation index (AIX)¹. These short-term changes may foster progression of cardiovascular disease if they recur on a chronic basis. In other contexts, these cardiovascular changes are induced by sympathetic nervous system activation. Therefore, we hypothesize that catecholamine release during sleep leads to increased heart rate, blood pressure, AIX, and altered metabolism. In this project we will examine whether OSA-related cardiometabolic changes during sleep can be prevented by beta blockade.

Design: Double-blind, crossover RCT of Propranolol LA vs. Placebo taken before sleep in patients with moderate-severe OSA. Participants will be CPAP-adherent patients who will temporarily discontinue CPAP for 3 nights prior to each visit, approximately 1 week apart. During sleep we will collect a full sleep study (oximetry, sleep staging, respiratory flow, muscle movements), IV blood samples (every 30 min). In the morning following each study, participants will undergo vascular assessment (endoPAT testing).

Sample size: In a preliminary study (n=6), Median individual heart rate during sleep \pm (SD) was 62.2 (9.2) with [OSA+placebo] and this decreased by 6.7 BPM with [OSA+propranolol]. To detect a 10% difference (reduction of 6.2 beats/min) at a power of 80% at a significance threshold of 0.05, using a one-tailed comparison, yields a sample size of 16 participants. Since we have already enrolled 5 subjects, we require 11 additional subjects. Assuming 20% dropout, we will enroll 14 additional subjects, a total of 19 participants.

Primary outcome: Median of continuously measured heart rate during sleep.

Secondary outcomes:

- augmentation index (normalized to 75 beats/min),
- heart rate variability metrics (HR standard deviation, min/max, 5th or 95th percentile)
- OSA severity (AHI, oximetry, event duration)
- sleep architecture (percent of each sleep stage during the night)
- Blood pressure
- metabolism (FFA, glucose, insulin).

Blinding:

As this is a double-blind study, above metrics will be calculated for each visit with only knowledge of visit number and not drug/placebo assignment. After these parameters have been derived, the research pharmacy will un-blind the biostatistician ([name]) and PI ([name]) to drug arm assignment to apply appropriate statistical tests, as described below.

Analysis:

For the primary analysis, we will derive summary metrics per night, per participant (i.e. median HR per night). Median heart rate per night will be compared between drug and placebo nights in a paired framework using paired student's T tests. Similar methods will be used to compare secondary outcomes. Some metrics will require additional derivation. For example, heart rate variation will be expressed as coefficients of variation, min/max and lower (5th) and upper (95th) percentiles, and visualized with Poincare plots as performed by collaborators at Johns Hopkins ².

Exploratory Analyses:

Since several outcomes involve time series data (e.g. heart rate, oxygen level during sleep, apnea-hyponea index) we will also evaluate trajectories of these metrics over time, and to detect potential drug x time interactions (i.e. the within night trajectories may vary depending on whether propranolol was received). For example, propranolol may have progressive effects over the course of the night as the drug is absorbed. For these time series analyses, we will reduce continuous metrics into 30-minute average bins (other bin sizes may also be trialed depending on clinically relevant time domains of the outcome). Mixed effects linear models will be used to compare these parameters using drug as the fixed factor, with a random effect for each subject. We will additionally incorporate time in the analysis using mixed effects models with time as a covariate and including a drug*time interaction. Random slopes and intercepts will be used in these regressions.

We anticipate that propranolol will significantly decrease heart rate. Propranolol may have effects on other outcomes (such as blood pressure or augmentation index), mediated by heart rate. We will examine these potential associations in linear regression (for example, change in HR versus change in blood pressure).

REFERENCES

1. Chopra, S. et al. Obstructive Sleep Apnea Dynamically Increases Nocturnal Plasma Free Fatty Acids, Glucose, and Cortisol During Sleep. *J. Clin. Endocrinol. Metab.* **102**, 3172–3181 (2017).
2. Kim, L. J., Pho, H., Pham, L. V. & Polotsky, V. Y. Isocapnic CO₂ administration stabilizes breathing and eliminates apneas during sleep in obese mice exposed to hypoxia. *Sleep* zsac243 (2022) doi:10.1093/sleep/zsac243.
